8.4.4 Reporting of Pregnancy

If any pregnancy occurs in a study subject, the PI will be notified immediately and the IRB will be notified within 3 days of discovery of the pregnancy. No data regarding safety or efficacy of Mavyret in pregnant women are available. Standard of care medications utilized for lung transplant recipients have known contraindications in pregnancies therefore any pregnancies will need to be managed as per standard of care with the lung transplant team. Counseling of pregnant subjects with regard to the risks of continuing versus discontinuing Mavyret will occur with patients once counseling with regard to the contraindications of the standard of care transplant medications has occurred.

8.5 Study Halting Rules

Further enrollment of study subjects will be halted under the following conditions:

- Any patient death occurs and is deemed related to the intervention
- Any SAE deemed related to acute HCV infection occurs
- Any SAE deemed related to Mavyret occurs

The PI will inform the IRB and the DSMB within 24 hours of any of these events. The DSMB and study team will convene an emergency meeting as described below. The DSMB will provide recommendations for proceeding with any further enrollment. Patients who are already enrolled and receiving Mavyret

CONFIDENTIAL

treatment will continue to receive treatment unless the DSMB determines that an alternate course of therapy should be pursued for already-enrolled subjects.

8.6 Safety Oversight

It is the responsibility of the Principal Investigator to oversee the safety of the study. This safety monitoring will include careful assessment and appropriate reporting of adverse events as noted above, as well as the construction and implementation of a site data and safety-monitoring plan. Medical monitoring will include a regular assessment of the number and type of serious adverse events.

Safety oversight will be under the direction of a DSMB. This DSMB committee for this study will be comprised of individuals with expertise in transplantation, hepatology, infectious diseases and the treatment of hepatitis C, and ethics. These individuals will be:

[name] (DSMB Chair) –Pediatric Infectious Disease [name] – Expert in Medical Ethics

[name] – Transplant Nephrologist
[name] – Pulmonologist
[name] – Pulmonologist
[name] – Hepatologist

The DSMB Charter with specific outlines of DSMB roles and responsibilities is uploaded as a separate attachment in Research Navigator. The DSMB will be notified of all AEs and SAEs as outlined above in 8.4.1 and 8.4.2. Regular meetings of the DSMB and the study team will occur on a quarterly basis to review non-emergent AEs and SAEs. The minimum group required to constitute an adequate DSMB-study team meeting will be (either in person or by teleconference): at least 4 of the DSMB members listed above, the PI, and at least one coinvestigator. At quarterly meetings the DSMB will evaluate cumulative participant safety data and make recommendations regarding the safe continuation of the study.

The DSMB and study team will meet on an emergency basis in the following instances:

- Any SAE occurs that is unexpected and deemed related to the study intervention
- Any unanticipated problem occurs that is both serious and deemed related to the study intervention
- Any treatment failure occurs or drug resistant HCV strain is identified, and a rescue plan with alternate therapy is required

Emergency meetings will occur within one business day of the above-described event occurring or being recognized. Any event that prompts an emergency DSMB-study team meeting will be reported to the IRB within 24 hours of the event occurring or being recognized.

9 Clinical Monitoring

Clinical site monitoring is conducted to ensure that the rights and well-being of human subjects are protected, that the reported trial data are accurate, complete, and verifiable, and that the conduct of the trial is in compliance with the currently approved protocol/amendment(s), with GCP, and with applicable regulatory requirement(s).

10 Statistical Considerations

10.1 Statistical and Analytical Plans (SAP)

As this is a single-arm observational study, no SAP will apply.

CONFIDENTIAL

10.2 Statistical Hypotheses

We hypothesize that 100% of patients who develop HCV viremia will achieve SVR after completing an 8-week course of Mavyret treatment.

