4.2 Study Endpoints

4.2.1 Primary Study Endpoints

The primary endpoint will be percentage of patients with sustained virologic response after treatment for HCV after lung transplant. This endpoint was chosen as primary because it will enable us to evaluate the safety of transient exposure to HCV at the time of lung transplantation. The expectation is that all patients who develop HCV viremia will achieve SVR (cure) following treatment with Mavyret.

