5.7.2 Handling of Participant Withdrawals or Termination

Discontinuation of the study agent is not anticipated, as this will place patients at risk to develop acute or chronic HCV. For patients who do elect to discontinue the study agent Mavyret due to intolerance or SAEs/AEs, the following steps will be taken:

- Hepatology consultation to guide management, which could include:
- Continued surveillance for evidence of HCV viremia in patients who had cleared their viremia
- Conversion to an alternate HCV treatment that can be tolerated by the patient

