7.6 Rescue Medications, Treatments, and Procedures

In the event that a subject fails to achieve SVR with Mavyret, rescue therapy with other marketed agents approved for the treatment of HCV will be administered. The rescue treatment will be determined based on genotyping and resistance testing, and the choice of drug(s) used will be prescribed under the direction of a transplant hepatologist and/or transplant infectious diseases physician.

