10.4.2 Analysis of the Primary Efficacy Endpoint(s)

The primary endpoint will be percentage of patients with sustained virologic response after treatment for HCV after lung transplant.

We expect that 100% of patients who are treated will achieve SVR. SVR will be defined as the absence of detectable HCV RNA Quantitative (PCR) testing 3 months after the completion of the treatment course. Any failure of therapy will be considered significant and will result in the halting of further enrollment until further discussed by the safety monitors and the IRB.

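### The primary SVR percentage has inconsistent denominators and no defined outcome for patients who die, stop early or are converted to another agent, which permits a completers-only figure tilted toward 100%

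*Combined protocol and SAP*

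**What the plan says.** The primary endpoint in Section 4.2.1 is the "percentage of patients with sustained virologic response after treatment for HCV after lung transplant". It names neither the drug nor the set of patients. The expected 100% is then attached to three groups:

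- **Section 4.2.1:** "all patients who develop HCV viremia will achieve SVR (cure) following treatment with Mavyret", that is, every viremic recipient.
- **Section 10.2:** "100% of patients who develop HCV viremia will achieve SVR after completing an 8-week course of Mavyret treatment", that is, viremic recipients with completion of the course as a condition.
- **Section 10.4.2:** "We expect that 100% of patients who are treated will achieve SVR", that is, everyone treated.

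Section 10.4.2 also fixes the timing: "SVR will be defined as the absence of detectable HCV RNA Quantitative (PCR) testing 3 months after the completion of the treatment course".

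Section 5.7.2 foresees that Mavyret may be stopped and lists as one option "Conversion to an alternate HCV treatment that can be tolerated by the patient". It does not say how the primary outcome is then scored. Section 10.3 lists variables and defines no analysis population. Section 10.1 states that no SAP applies, so no other document is named to settle the matter.

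**The concern.** A result timed from course completion does not exist for someone who never completes. If such patients fall out of both numerator and denominator, the percentage describes only those who survived and tolerated eight weeks of treatment, and it stays at 100% however many are lost. Section 4.2.1 says the endpoint was chosen to evaluate the safety of transient HCV exposure, so losing deaths and intolerance from it would defeat that purpose.

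One patient matters here. Section 10.5 regards a single treatment failure as a significant departure from expectation, and Section 10.4.2 halts enrollment on any failure of therapy. How one patient is classified can change both the conclusion and the conduct of the trial.

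**Working it through.** **Inputs from the documents.** Enrollment 20 and about 70% viremic and treated (Section 10.5); 7 treated (also Section 10.5); drug-related permanent discontinuation 0.1% (Section 2.4.1); 8-week course (Section 6.1.8); RNA tests weekly to POW 12, then at POW 24 and POW 52, each ±14 days (Section 19).

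**Step 1. The plan's own denominator.** 20 × 0.70 = 14, not 7. The figure 7 would need 70% of 10 or 35% of 20, and neither is stated. Section 2.1 estimates that one-third of HCV-positive donors are non-viremic, which gives 20 × 2/3 = 13.3. The 7 is not reproduced, so both sizes are carried forward.

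**Step 2. Effect of one or two losses.** A loss here is a patient who dies before the SVR test, or who stops and has no qualifying result on Mavyret. All others are assumed to reach SVR. Intervals are exact (Clopper-Pearson): the lower limit is the 0.025 quantile of Beta(x, n−x+1) and the upper limit the 0.975 quantile of Beta(x+1, n−x), with the upper limit set to 100% when x = n.

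| Treated | Losses | Completers only | All treated, loss = non-SVR |
|---|---|---|---|
| 14 | 0 | 14/14 = 100% (76.8–100) | 14/14 = 100% (76.8–100) |
| 14 | 1 | 13/13 = 100% (75.3–100) | 13/14 = 92.9% (66.1–99.8) |
| 14 | 2 | 12/12 = 100% (73.5–100) | 12/14 = 85.7% (57.2–98.2) |
| 7 | 0 | 7/7 = 100% (59.0–100) | 7/7 = 100% (59.0–100) |
| 7 | 1 | 6/6 = 100% (54.1–100) | 6/7 = 85.7% (42.1–99.6) |
| 7 | 2 | 5/5 = 100% (47.8–100) | 5/7 = 71.4% (29.0–96.3) |

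One patient moves the all-treated figure by 1/14 = 7 points or 1/7 = 14 points. The completers-only figure does not move.

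**Step 3. Conversion for intolerance.** If one of 14 is switched to another agent and cured, the result is 14/14 = 100% when that cure counts and 13/14 = 92.9% when the endpoint is SVR on Mavyret. Section 10 does not say which applies.

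**Step 4. How likely is a loss?** At the 0.1% drug-related rate, expected stops are 14 × 0.001 = 0.014, and the chance of at least one is 1 − 0.999^14 = 1.4%. Death and loss to follow-up come on top, and the documents give no rate for either. Purely as an assumed range, a per-patient loss probability of 3%, 5% or 10% gives 1 − (1 − q)^14 = 35%, 51% or 77%.

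**Step 5. Can the outcome be observed on schedule?** A course started at POW s ends at s + 8 and reaches three months (about 13 weeks) at s + 21. The POW 24 window closes at POW 26, so s + 21 ≤ 26 requires s ≤ 5. A later start has its first scheduled qualifying test at POW 52. A start at POW 8, for example, reaches three months near POW 29, between tests. Any rule for a missing result has to allow for this.

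**The case against.** A reader might infer that the plan drops deaths and early stoppers by definition. It does not. No section excludes them, Section 10.2 is a hypothesis rather than an analysis rule, and the reference in Section 10.4.2 to treated patients could keep them in the denominator as non-SVR. Their outcome is undefined; they are not removed.

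A reader might also infer that rescue cures will count as successes, because the endpoint wording names no drug. Most of the text points the other way. Sections 4.2.1 and 10.2 tie SVR to Mavyret. Section 7.6 begins "In the event that a subject fails to achieve SVR with Mavyret, rescue therapy with other marketed agents", so a rescued patient has already failed. Section 10.4.1 reports treatment failure as its own percentage, and Section 10.4.2 halts enrollment on any failure. Only conversion for intolerance under Section 5.7.2 is really open.

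The three groups largely coincide if only viremic recipients are treated, as Section 2.1 and the Section 19 footnote say. Deaths are visible elsewhere: one-year survival is a secondary endpoint, and Section 10.4.6.1 halts enrollment on any death. Nor is the direction of bias fixed, since reading the denominator as all 20 transplanted would give 14/20 = 70%. The study is a small descriptive pilot. Finally, Sections 7.2.4 to 7.3.6, including the withdrawal visit, are absent from the text reviewed, so a handling rule there cannot be ruled out.

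All of this limits the claim. It does not supply the missing rule: Section 10 has none, and reporting survival separately does not say how a death enters the SVR percentage.

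**Conclusion.** The point holds as a gap that permits a favourable analysis, not as a bias built into the definition. The denominators are inconsistent, and death, early stop, conversion and missing SVR have no assigned outcome. The completion condition in Section 10.2, taken with the timing in Section 10.4.2, supports a completers-only figure.

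The size for one loss is 100% against 93% with 14 treated, or 100% against 86% with 7. This assumes that everyone else reaches SVR. How often it would occur cannot be derived from the documents; at their drug-related discontinuation rate intolerance alone is unlikely to cause it, so death or loss before the test is the main route. With no SAP and one failure treated as decisive, the rule should be settled before results are seen.

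**What to change.** In Sections 4.2.1, 10.2 and 10.4.2:

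1. State one primary set: all recipients with post-transplant viremia, with any who were never dosed shown separately. Remove completion of the course as a condition in Section 10.2.
2. Define SVR on the first Mavyret course as undetectable HCV RNA at the first scheduled test at least three months after the last dose, which is POW 24 or POW 52 depending on start date.
3. Count death before that test, conversion or rescue, and absence of a qualifying RNA result as non-SVR. A recipient first found viremic at POW 52 has no later scheduled test, so the text should say how that case is shown.
4. Report an exact 95% interval. Give completers-only SVR, and cure including alternate or rescue therapy, as supportive figures.

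Reconcile 7 with 14 treated in Section 10.5. Also reconcile the passages on who is treated: Section 2.4.1 and the study-agent and key-procedure entries of the Protocol Summary (all patients) against Section 2.1 and the Section 19 footnote (after viremia is detected). The primary set must match whatever results.

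The cost is wording, with no new data needed for the main rule. The headline percentage may be slightly less favourable, and late starters are scored only at POW 52.

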10.3 Analysis Datasets

Subjects will be entered into a study subject dataset which includes de-identified information. This will include: donor and recipient demographic data, donor HCV RNA quantitative (PCR), serology, and genotyping information, and results of all recipient HCV RNA quantitative (PCR), serologic, and genotyping data obtained throughout the course of the study.

10.4 Description of Statistical Methods

Since the anticipated study population will be a small size, statistical analyses will be limited to descriptive statistics. For patients who develop post-transplant viremia we will be able to compare our HCV cure rates to those that are expected for patients who receive treatment with these agents for chronic HCV.

10.4.1 General Approach

The study design will be single arm, open label. Descriptive statistics will include:

- Incidence HCV viremia post-transplant (percentage)
- Time course of exposure to development of clinically detectable viremia in those who develop viremia (median time to viremia with standard deviations)
- Incidence of sustained clearance of HCV (cure) after treatment of viremia (percentage)
- Time course of clearance of viremia after treatment initiation (median time to clearance with standard deviations)
- Incidence of treatment failure/treatment resistant strains of HCV (percentage)
- Characterization of distribution of HCV genotypes in patients who develop viremia (percentages)
Comparison of treatment failure rates to expected treatment failure rates for the treatments used (p value for significance will be set at $p < 0.05$ and two-tailed t-test will be used)

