3.2 Secondary Objectives (if applicable)

Secondary objectives will include characterization of the incidence of HCV viremia in recipients whose lung donors were HCV positive.

For those who develop viremia we will also characterize the time course of the development of viremia, and subsequent clearance of viremia after treatment.

CONFIDENTIAL

4 Study Design and Endpoints

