10.5 Sample Size

20 patients are expected to enroll in this trial.

We expect that less approximately 70% of patients will develop evidence of HCV infection transmitted from the HCV-positive donor and will be treated for HCV infection. We expect that 100% of the patients who are treated for HCV viremia will achieve SVR.

This is a single-arm study with no comparison group. The power to detect a difference in observed versus expected depends upon the true efficacy of the therapy. The reported efficacy of the therapy is 98%.

With an estimated 7 patients who will be treated, a single treatment failure will be regarded as a significant deviation from the expected outcome.

CONFIDENTIAL

11 Source Documents and Access to Source Data/Documents

Source data is all information, original records of clinical findings, observations, or other activities in a clinical trial necessary for the reconstruction and evaluation of the trial. Source data are contained in source documents. Examples of these original documents, and data records include: hospital records, clinical and office charts, laboratory notes, memoranda, subjects' diaries or evaluation checklists, pharmacy dispensing records, recorded data from automated instruments, copies or transcriptions certified after verification as being accurate and complete, microfiches, photographic negatives, microfilm or magnetic media, x-rays, subject files, and records kept at the pharmacy, at the laboratories, and at medico-technical departments involved in the clinical trial. It is acceptable to use CRFs as source documents.

If this is the case, it should be stated in this section what data will be collected on CRFs and what data will be collected from other sources.

The study case report form (CRF) is the primary data collection instrument for the study. All data requested on the CRF must be recorded. All missing data must be explained. If a space on the CRF is left blank because the procedure was not done or the question was not asked, write "N/D". If the item is not applicable to the individual case, write "N/A". All entries should be printed legibly in black ink. If any entry error has been made, to correct such an error, draw a single straight line through the incorrect entry and enter the correct data above it. All such changes must be initialed and dated. **DO NOT ERASE OR WHITE OUT ERRORS.** For clarification of illegible or uncertain entries, print the clarification above the item, then initial and date it.

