- Pregnant Partner Contact Card
- Sample Willingness to Participate Form
- Sample Fact Sheet
- SOP for specimen handling
- Accreditation for the Transplant Laboratory
- Specimen collection and shipping instructions for Quest Laboratories

CONFIDENTIAL

19 Schedule of Events: Surveillance post-transplant with an 8 weeks MAVYRET treatment phase included

Activity	Screening visit (POD-365 to -1)	SURVEILLANCE PHASE					
		POD0	POW1 (+/- 2 day)	POW2 (+/- 3 days)	POW3 (+/- 3 days)	POW4 (+/- 5 days)	POW5 (+/- 5 days)
Study team procedures							
Acknowledgement of willingness to participate and provision of fact sheet	X						
Medical History		X					
Physical Exam		X					
Height		X					
Weight		X					
Vitals signs		X					
Review all donor and recipient inclusion/exclusion criteria		X					
Signing of informed consent		X					
Study specific interventions							
Lung transplant operation		X					
Mavyret treatment (Start and follow up)		X ¹					
Study specific laboratory tests							
Donor serum HCV genotyping		X					
Recipient serum HCV genotyping		Any time during the study (x1) once there is documentation of positive HCV RNA Quantitative (PCR)					
HCV RNA Quantitative (PCR)	X	X ²	X	X	X	X	X
HCV serology (HCV Ab)	X	X ²	X	X	X	X	X

X¹ Mavyret will be initiated post lung transplantation once a viral load is detected

X² If screening lab(s) specifically HCV RNA Quantitative (PCR) and HCV serology (HCV Ab) are performed 14 days or less prior to POD 0, those labs will not be repeated at the POD 0 timepoint.

CONFIDENTIAL

This material is the property of the NYU School of Medicine and Langone Medical Center. Do not disclose or use except as authorized in writing by the study sponsor
Interventional Template Version: 28 APR 2017

Activity	SURVEILLANCE PHASE			POW9 (+/- 5 days)	POW10 (+/- 5 days)	POW11 (+/- 5 days)
	POW6 (+/- 5 days)	POW7 (+/- 5 days)	POW8 (+/- 5 days)			
Study team procedures						
Study specific interventions						
Mavyret treatment (Start and follow up)	X ¹					
Study specific laboratory tests						
Recipient serum HCV genotyping	Any time during the study (x1) once there is documentation of positive HCV RNA Quantitative (PCR)					
HCV RNA Quantitative (PCR)	X	X	X	X	X	X
HCV serology (HCV Ab)	X	X	X	X	X	X

Activity	POW12 (+/- 5 days)	POW 24 - Interim assessment visit (+/- 14 days)	POW 52 - Final assessment visit (+/- 14 days)
Study team procedures			
Mavyret treatment (Start and follow up)	X ¹		
Medical History			X
Physical Exam			X
Height			X
Weight			X

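### Time to viremia and time to clearance are to be summarised as a median with a standard deviation, which does not measure spread around a median and which one late case can dominate in so small a sample.

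*Combined protocol and SAP*

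**What the plan says.** Section 10.4.1 of the combined protocol and SAP lists the descriptive statistics. For time to viremia, among those who become viremic, it specifies "median time to viremia with standard deviations". For clearance after the start of treatment it specifies "median time to clearance with standard deviations". The list contains no mean, interquartile range, range or Kaplan-Meier summary for either time, and no other section supplies one.

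No further analysis stands behind these summaries. Section 10.1 states: "As this is a single-arm observational study, no SAP will apply". Section 10.4 adds that "statistical analyses will be limited to descriptive statistics". The two times serve a secondary objective in Section 3.2: "For those who develop viremia we will also characterize the time course of the development of viremia, and subsequent clearance of viremia after treatment". They are not among the secondary endpoints listed in Section 4.2.2.

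The schedule of events in Section 19 shows HCV PCR weekly from POW1 to POW12, then at POW24 and POW52, each of the last two within 14 days. Section 10.4.8 plans to evaluate individual data on how viremia develops and clears.

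**The concern.** A median and a standard deviation answer different questions. The median is the middle value. The standard deviation is built from squared distances to the mean, and here the mean is not reported. A reader given only these two numbers cannot tell where the middle half of the patients lay or how late the latest case was.

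Two features of the design make this more than a matter of taste. The number of viremic patients will be small, and the PCR schedule jumps from POW12 to POW24 and then to POW52. A patient first found positive at a scheduled visit after POW12 therefore enters the data at about week 24 or week 52. Because distances are squared, one such value can supply most of the standard deviation and leave the median where it was. At stake is how clearly the time course, a stated secondary objective, is described.

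**Working it through.** The plan gives no expected time, spread or precision for either outcome, so there is no figure of its own to reproduce. The check is how far one case can move each summary on the plan's visit schedule.

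**Inputs from the documents**

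- Enrolment (Section 10.5): "20 patients are expected to enroll in this trial".
- Viremia rate (Section 10.5): "We expect that less approximately 70% of patients will develop evidence of HCV infection transmitted from the HCV-positive donor". This gives 0.70 × 20 = 14.
- Section 10.5 also estimates 7 treated patients, which does not follow from 70% of 20. Those two figures need reconciling. Both are used here, and the point does not depend on which is meant.
- Scheduled PCR (Section 19): weekly to POW12, then POW24 and POW52.

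**Assumed: every event time below.**

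**Formulas.** SD = √[Σ(x − mean)² / (n − 1)]. Quartiles use linear interpolation.

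**Worked example, onsets clustered in weeks 1 and 2, n = 14.** Eight cases at week 1, five at week 2 and one last case.

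- Last case at week 3: mean = 21/14 = 1.5. Sum of squares = 8(0.25) + 5(0.25) + 2.25 = 5.5. SD = √(5.5/13) = 0.65.
- Last case at week 24: mean = 42/14 = 3. Sum of squares = 8(4) + 5(1) + 441 = 478. SD = √(478/13) = 6.06. The one late case supplies 441/478 = 92% of the sum of squares.
- Ratio: 6.06/0.65 = 9.3. In both sets the median is 1 and the interquartile range (IQR) is 1 to 2.

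**Other assumed sets, time to viremia.** Only the last case moves.

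| Set | Last case moved | SD (weeks) | Ratio | Median and IQR |
|---|---|---|---|---|
| n = 14: five at week 1, five at 2, two at 3, one at 4, plus last | week 4 to 24 | 1.07 to 5.97 | 5.6 | 2.0 (1.0 to 2.75), unchanged |
| n = 7: three at week 1, two at 2, one at 3, plus last | week 4 to 24 | 1.15 to 8.47 | about 7 | 2.0 (1.0 to 2.5), unchanged |
| n = 14: one at each of weeks 1 to 12, a second at 12, plus last | week 12 to 24 | 3.87 to 5.83 | 1.5 | 7.5 (4.25 to 10.75), unchanged |

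The third set is the least favourable to the point. Even there the POW24 case supplies 57% of the sum of squares. If the last case is first found at POW52 instead, the SD in that set becomes 12.58, a ratio of 12.58/3.87 = 3.3.

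**Time to clearance, weeks from treatment start, n = 14.** One case at week 1, three each at weeks 2, 3 and 4, two at week 5, one at week 6, plus last. Moving the last case from week 6 to week 12 raises the SD from 1.55 to 2.69, and moving it to week 24 raises it to 5.68. The median stays at 3.5 and the IQR at 2.25 to 4.75.

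**The case against.** The strongest reply is that a standard deviation beside a median is a correctly computed number with an unsuitable partner, and that little hangs on it. Much of that stands. No test, sample size, halting rule or primary result uses this quantity. Section 10.4.8 already plans to look at individual kinetics, and Section 10.3 keeps every recipient PCR result. With at most 20 patients, an IQR could be produced at any time.

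A reader might go further and infer that the plan will produce faulty error bars or impossible negative times. The documents do not support that. They plan no figure and no interval of median plus or minus one standard deviation. A negative value appears only if a reader subtracts one number from the other, and then only in some of the assumed data sets.

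A reader might also take the nine-fold change as the expected effect, or right skew as established. Neither is documented. A POW24 first positive needs a patient who is negative at every weekly test and positive later, and nothing in the plan says that this is expected. Nor can it be said that no PCR falls between the late visits: the contents list a Section 7.3 with intermediate and unscheduled visits, and its text was not available for this check.

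For clearance the late outlier is less natural. A patient who starts the 8-week course in week 1 or 2 finishes by about week 10, while PCR is still weekly.

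None of this repairs the pairing in Section 10.4.1, which remains the planned summary.

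**Conclusion.** The point holds as a mismatch in the stated summary. The standard deviation does not describe spread around the median, for either time, whatever the data turn out to be. Its sensitivity to one case is a second reason to replace it. In the assumed times to viremia with n = 14, moving the last case to POW24 changes it by a factor of about 1.5 to about 9, and with n = 7 by about 7. The median and IQR do not move in any of these sets. The direction follows from how the statistic is built; the size rests wholly on assumed event times. The primary endpoint, the percentage with sustained virologic response, is untouched. Severity is the lowest.

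**What to change.** In both bullets of Section 10.4.1, replace the standard deviations with the interquartile range and the range. The range keeps any late case in view, so nothing is hidden. In the individual tabulation of Section 10.4.8, list for each viremic patient the week of the last negative and the first positive PCR, so that the reader sees how wide the detection interval was, above all after POW12. A patient who never clears has no clearance time, so the number of such patients should stand beside the clearance summary.

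The cost is a wording change. It needs no new visits, tests or patients, and should be made before the data are summarised.
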